5. Nielsen, T., et al., Maternal and infant characteristics associated with maternal opioid overdose in the year following delivery. *Addiction*, 2019.

2. * Describe the study hypothesis and/or research questions. Use lay language whenever possible.

1. How feasible and acceptable is the technology-based intervention with content on NOWS, child welfare interactions, and the postpartum transition compared to a brochure for pregnant patients receiving MOUD?

We hypothesize that integration of the technology based intervention into a busy prenatal clinic will be as feasible as the brochure and more acceptable to patients.

2. How effective is the intervention for improving exploratory outcomes (i.e., mental health, recovery, functioning, and quality of life)?

3. * Describe the study's specific aims or goals. Use lay language whenever possible.

The primary objectives of this RCT are to assess the feasibility and acceptability of the technology-based educational intervention with content on NOWS, child welfare interactions, and the postpartum transition compared to a brochure for pregnant patients receiving MOUD.

Additional exploratory objectives are to evaluate intervention effectiveness on improving outcomes (i.e., mental health, recovery, functioning, and quality of life).

4. * Describe the scientific benefit or importance of the knowledge to be gained:

Integrated treatment programs for pregnant and parenting women with OUD, like ours at VCU, need better educational tools specific to the postpartum transition. The proposed study will provide critical feasibility and acceptability data to improve the novel patient education materials and inform future studies evaluating clinically applicable patient centered interventions focused on the mother-infant dyad affected by OUD. Ultimately, implementation of clinically applicable patient-centered interventions focused on the mother-infant dyad could have broad positive impacts on the long-term health of families in the opioid crisis.

5. * Describe any potential for direct benefits to participants in this study:

Participants may gain additional knowledge to help them prepare for the pregnancy to postpartum transition and take care of their recovery.

6. * Describe any potential for direct social impact in this study . For example, any engagement with specific communities to respond to community-identified needs, or ways the study will strengthen the well-being of the specific communities if applicable:

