If participants are unable to complete the any part of the study in person at the clinic OR they prefer to complete the study visits remotely, they will have the option to complete study visits by a confidential link to a unique redcap survey that will be emailed or texted to them at their preferred email or phone number (which will be confirmed with them before emailing the link) from the research assistant who will also call the patient over the phone for some questions.

No recruitment or consent procedures will be done by the PI who is clinical director of the OB MOTIVATE program.

**The IRB-approved study flyer will be posted in community-based addiction treatment and OB/GYN clinics. The study research assistant will contact potential participants who provide contact information within one week of providing information. The IRB-approved remote recruitment scripts will be used by the research assistant to assess potential participant interest in study participation and confirm eligibility. Phone recruitment will be conducted by a research assistant who is a member of the research team. If the research staff is unable to get in touch with the potential participant by phone, then eligible potential participants will be sent a study notification email that includes information about the study with a note that the research staff will follow-up with a phone call within one week to assess their interest in participating. This email will also provide an option to opt-out of further contact. Eligible and interested subjects will undergo the informed consent process and complete the baseline assessment (Study visit 1). Subjects who are eligible and decline participation will be asked to answer 5 demographic questions by self-administration of the 5 questions.

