3. Potential participants will be called and/or emailed by the research assistant (up to 4 times over 10 weeks) or approached in the clinic when they arrive for a scheduled clinic appointments while waiting to see their provider in the private exam rooms. If the potential participant does not answer the phone, the research assistant will leave a generic voicemail without any identifying information (i.e., "This is (RA name) calling from VCU health about potential participation in a research study. If you are interested in learning more, please return the call to XXX-XXX-XXXX"). When the RA talks to the potential participants, they will confirm their eligibility for the study verbally using the eligibility form (see uploaded recruitment scripts).

**Potential participants who use the recruitment flyer QR code to provide contact information will be called and/or emailed by the research assistant (up to 4 times over 10 weeks). If the potential participant does not answer the phone, the research assistant will leave a generic voicemail without any identifying information (i.e., "This is (RA name) calling from VCU health about potential participation in a research study. If you are interested in learning more, please return the call to XXX-XXX-XXXX"). When the RA talks to the potential participants, they will confirm their eligibility for the study verbally using the eligibility form (see uploaded recruitment scripts).

6. * Does this study have a separate protocol document (i.e. a multisite or sponsor's protocol) that contains a detailed description of the study's methodology?

Yes
 No

7. * Upload the separate protocol document, and in the response below, provide all of the following information:

1. Identify which specific sections of the protocol describe the study design and procedures.
2. A statement explaining the study design
3. A lay language overview of all research activities/procedures
4. For multisite studies, a description of whether there are any local changes to the protocol's procedures, and if so, what those changes are (i.e. different, omitted, or additional procedures)
5. Any necessary clarifications of the protocol's content (i.e. what local standard of care or routine practice is)

1. Entire Standard Operating Procedures (SOP) document

2. Pilot feasibility randomized controlled trial comparing technology-based modules (intervention) to a brochure (control)

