3. Following consent, participants will complete the first study visit, a baseline assessment (electronic survey & brief RA questions). Then participants will be randomized (1:1) to either the technology-based modules (intervention) group or the brochure (control) group. Randomization and intervention introduction can be completed at the same time of the other first study visit procedures (ie, pre-survey) or as a supplemental unpaid visit based on participant preference (ie, if the participant wants to complete the pre-survey remotely and the intervention introduction in person). Participants will be provided access via email/text to the modules or the electronic brochure (based on randomization) for three weeks. Following the 3-week study intervention period, participants will complete two follow-up study visits (electronic survey & brief RA questions): 1) during pregnancy within two weeks of intervention timeframe (Study visit 2) and 2) within 4-8 weeks postpartum (Study visit 3). Enrolled, randomized participants not completing Study visit 2 within 5 weeks of study condition introduction, but wishing to do so, will be reviewed by the PI on a case-by-case basis for the opportunity of continued study participation. Specifically, if the participant is no longer pregnant, study continuation will not be allowed; if still pregnant, the PI will consider the option of study continuation (e.g., completion of follow-up visit 1) for the participant. For each study visit, we will also obtain health information (as per secondary data page and uploaded document) via the health record after participants have agreed to the HIPAA authorization in the consent form. Participants will be compensated \$20 per study visit (up to \$60 total).

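### As most naturally read, the late-visit rule ends the study for a willing randomised participant who is no longer pregnant, although her postpartum visit could still be done

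*Combined protocol and SAP*

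**What the plan says.** The overview of procedures in the combined protocol and SAP (Study Procedures, question 7, item 3) gives participants three weeks of access to the modules or the brochure. Two follow-up visits come after that. Study visit 2 (also called follow-up visit 1) takes place during pregnancy, within two weeks of the access period. Study visit 3 takes place 4 to 8 weeks postpartum.

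The late-visit rule applies to anyone randomised whose visit 2 is still outstanding five weeks after she was introduced to her condition. About such participants the text says: "but wishing to do so, will be reviewed by the PI on a case-by-case basis for the opportunity of continued study participation". It has two branches:

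- No longer pregnant: "Specifically, if the participant is no longer pregnant, study continuation will not be allowed".
- Still pregnant: "the PI will consider the option of study continuation (e.g., completion of follow-up visit 1) for the participant".

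Three other places bear on the point.

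- The answer on recruitment (question 5) offers remote completion to participants who cannot attend or prefer not to: "they will have the option to complete study visits by a confidential link to a unique redcap survey".
- For the full design, item 1 of question 7 points to the "Entire Standard Operating Procedures (SOP) document", which is not part of the supplied file.
- The aims (Background, Rationale and Goals, question 3) make feasibility and acceptability primary, and add: "Additional exploratory objectives are to evaluate intervention effectiveness on improving outcomes".

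**The concern.** Visit 3 happens after delivery by definition, so having delivered is no scheduling obstacle to it. Yet the rule turns having delivered, combined with a missed visit 2, into a reason to stop. Both are events after randomisation, and the rule is written for participants who still want to take part.

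Someone stopped this way has already missed visit 2, so visit 3 is her only remaining follow-up survey. For participants recruited from community treatment sites all data are self-reported (Secondary Data/Specimen Details, question 1), so no chart data would fill the gap. Visit 3 completion would also partly reflect the rule rather than participants' willingness, in a trial whose primary aims include feasibility. The supplied text does not say how such a stop is recorded, and it gives no criteria for the investigator's decision in the still-pregnant branch.

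**Working it through.** **1. The plan's own cut-off.** Three weeks of access plus a two-week visit window gives 3 + 2 = 5 weeks, which matches the stated 5 weeks.

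**2. Can the situation arise?** Entry is limited to less than 34 weeks' gestation, so the latest entry is 33 weeks 6 days. If introduction happens then, week 5 falls at 38 weeks 6 days. A delivery before that point with visit 2 not done meets the rule.

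**3. Is visit 3 still obtainable?** Let d be the day of delivery counted from introduction, from 0 to 35. At day 35 she is 35 − d days postpartum. The visit 3 window closes at day 56 postpartum, so 56 − (35 − d) = 21 + d days remain, which is 21 to 56 days. Less time remains if the review comes later, and none if it comes more than 8 weeks after delivery. The text sets no review date.

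**4. What is being decided?**

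- Broad reading: the subject of the review is continued participation in the study. In the still-pregnant branch, follow-up visit 1 appears only as an example of continuation. Visit 2 is already defined as a pregnancy visit, so a rule that merely barred it after delivery would add little.
- Narrow reading: the trigger is a missed visit 2 that the participant still wishes to do, and the only example given is that visit. The pregnancy condition then simply restates that visit 2 belongs to pregnancy.

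The broad reading fits the words better, but the text does not exclude the narrow one. Nothing supplied expressly keeps visit 3 open.

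**5. How many participants?** The documents give N = 30 (15 per arm) and the gestation limit. Everything else here is assumed:

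- gestation at delivery is normal, with (mean, SD) in weeks of (39, 1.8), (38.5, 2.0) or (38, 2.5);
- entry gestation g is uniform up to 33 weeks 6 days;
- visit 2 is scheduled at a time U, uniform over weeks 3 to 5, in a proportion c of participants, and is done only if the participant is still pregnant.

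With T the weeks from entry to delivery and F the delivery distribution:

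P(T < k) = [F(g + k) − F(g)] / [1 − F(g)], averaged over g

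P(delivered by week 5 without visit 2) = P(T < 5) − c × E over U of P(U < T < 5)

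For entry from 20 weeks, P(T < 5) is 4.68%, 7.11% and 10.52%, or 1.40, 2.13 and 3.16 of 30. The expected number of 30 who have delivered by week 5 without visit 2, at c = 0.8, is:

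| Earliest entry | (39, 1.8) | (38.5, 2.0) | (38, 2.5) |
|---|---|---|---|
| 12 weeks | 0.52 | 0.87 | 1.41 |
| 20 weeks | 0.83 | 1.37 | 2.22 |
| 26 weeks | 1.46 | 2.41 | 3.92 |

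The range is therefore about 0.5 to 3.9 of 30. For entry from 20 weeks, c = 0.6 gives 0.97 to 2.46 and c = 0.9 gives 0.76 to 2.11. Taking pregnancy status at week 7 instead, at c = 0.8, gives 1.41 to 2.89.

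These are upper figures within each scenario, because the rule applies only to those who still wish to do visit 2. At c = 1, where every woman still pregnant at her scheduled time completes the visit, the entry-from-20-weeks count is still about 0.7, 1.2 and 2.0. That is roughly 83% to 90% of the 80% figures. Most of the count is thus women who delivered before an in-window visit 2, rather than women who let the window pass while pregnant.

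**6. What does a loss do?** One participant is 1/30 = 3.3 points of overall retention and 1/15 = 6.7 points of one arm. For a between-arm mean difference, the 95% confidence interval half-width is t(0.975, n1 + n2 − 2) × √(1/n1 + 1/n2), in SD units: 0.748 at 15 v 15, 0.762 at 14 v 15, 0.777 at 14 v 14 and 0.810 at 13 v 13.

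**The case against.** The strongest reply is that the rule may only decide who can still do a pregnancy-only visit. On that reading no visit 3 data are lost and the text needs only clarifying. The passage is also a lay overview: the SOP is named as the place for design and procedures, and it may contain the visit 3 handling, the criteria for the investigator's decision and the recording of stops. Both points stand, so the concern has to remain conditional.

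The count is also open to challenge. It rests on assumed distributions, it is not reduced for willingness, and it consists mostly of women who delivered before visit 2 could take place. That too stands. They still meet the rule's wording, since they have not completed visit 2, but only if they wish to do it. The text is silent on those who do not.

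The effect is small as well. Effectiveness outcomes are exploratory, the content of the visit 3 survey is not supplied, and two losses widen the interval only from 0.748 to 0.777 SD.

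A reader might go further and infer that the rule biases the comparison of the arms, or that the plan definitely discards postpartum data. The documents support neither. Nothing shows that late visits or early deliveries differ by arm or in which direction any bias would run, and the wording leaves the narrow reading open.

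**Conclusion.** The concern holds in conditional form. On its more natural reading, the rule stops a willing randomised participant at a point when visit 3 is still obtainable, with 21 to 56 days of its window left at week 5. The number affected cannot be derived from the documents. Under the stated assumptions and 80% visit 2 completion it is at most about 0.5 to 3.9 of 30 by week 5, and any further stops by investigator decision in the still-pregnant branch cannot be estimated.

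The consequence is minor: some avoidable loss of exploratory follow-up, and a retention figure that mixes protocol-driven stops with drop-out. Confidence is moderate, because the SOP could settle the reading either way.

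**What to change.** Amend Study Procedures (question 7, item 3) and the SOP as follows.

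1. State that the pregnancy condition and the investigator's review govern visit 2 only, and that a missed or late visit 2 does not end follow-up.
2. State that every randomised participant who delivers and has not withdrawn is offered visit 3 at 4 to 8 weeks postpartum, whether or not visit 2 was done. The sponsor should state separately how participants with a pregnancy loss are handled, since the present wording also covers them.
3. Report retention with all randomised participants as the denominator, and show any protocol-driven stop by arm and reason, apart from drop-out.

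If the narrow reading was always meant, a brief clarification covers the first two items, apart from the statement on pregnancy loss.

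The cost is a short amendment and $20 per extra visit 3. Over the week-5 range that is 0.5 × $20 = $10 to 3.9 × $20 = $78 in total, plus $20 for any still-pregnant participant who would otherwise have been stopped. All of it stays within the planned $60 per participant. The downside is that some participants will have visit 3 without visit 2.

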4. N/A

5. N/A

8. * The IRB only reviews research activities, so indicate for each of the study activities described in the question above or in the protocol which activities are:

- Being performed exclusively for research purposes (i.e. they would not otherwise be done apart from this study) VERSUS.
- Alterations of routine activities/procedures (e.g. the study is altering the timing, frequency, method, location, amount, etc.) VERSUS.
- Being done for other purposes and whose data/results will be used secondarily in the study (e.g. standard medical or psychological tests, routine education practices, quality improvement initiatives, etc.).

See the help text for additional guidance

Participants will complete the three study visits and review the modules or brochure entirely for research purposes. Their medical care will proceed in same manner regardless study participation and study group condition.

9. If applicable, describe alternatives (research or non-research) that are available to potential participants if they choose not to participate in this study:

N/A

10. Upload any supporting tables or documents (e.g. protocol documents, figures/tables, data collection forms, study communications/reminders):

Upload ALL instruments/guides that will be used or that participants will experience (i.e. see, hear, complete), including measures, scripts/questions to guide interviews, surveys, questionnaires, observational guides, etc.:

Upload ALL recruitment and screening materials, including such as ads, flyers, telephone or in-person scripts, letters, email invitations, TelegRAM announcements, and postcard reminders, screening scripts, screening forms, and screening measures:

	Document Name	Document	Version	Date Modified	Uploaded By	Type	Approved
View	Project BETTER Consent Form Community-based recruitment	Community-based recruitment Project BETTER Consent Form_clean IRB 10.25.pdf	0.05	11/7/2022 10:47 AM	[name]	Consent/Assent/Information Sheet	Yes
View	Community-based Study Interest Form	StudyInterest_ProjectBETTERCom.pdf	0.01	10/31/2022 4:01 PM	[name]	Recruitment/Advertising	Yes
View	SOP	HM20023314 Project BETTER RCT SOP 10.31.22.docx	0.05	10/31/2022 3:59 PM	[name]	Research Protocol	Yes
View	Project BETTER Community-based recruitment email template	Project BETTER Community Recruitment Study Notification Email Template.docx	0.01	10/31/2022 3:58 PM	[name]	Recruitment/Advertising	Yes
View	Project BETTER Community-based recruitment script	Project BETTER Community Remote Recruitment Scripts.docx	0.01	10/31/2022 3:58 PM	[name]	Recruitment/Advertising	Yes
View	Project BETTER Community-based recruitment flyer	Project BETTER Community-based Flyer.docx	0.01	10/12/2022 5:00 PM	[name]	Recruitment/Advertising	Yes
View	Project BETTER RA Forms 3 Delivery Questions	Project BETTER Study Visit 3 Delivery Questions.docx	0.01	10/5/2022 2:33 PM	[name]	Research Measure	Yes
View	Eligibility Form	Revised 7.18.22 Project BETTER Eligibility Form.docx	0.02	7/18/2022 5:45 PM	[name]	Research Measure	Yes
View	In-person Recruitment Script	Revised 7.18.22 Project BETTER In Person Recruitment Scripts.docx	0.04	7/18/2022 5:44 PM	[name]	Recruitment/Advertising	Yes
View	Remote Recruitment Script	Revised 7.18.22 Project BETTER Remote Recruitment Scripts.docx	0.02	7/18/2022 5:43 PM	[name]	Recruitment/Advertising	Yes

Document Name	Document	Version	Date Modified	Uploaded By	Type	Approved
View Recruitment Flyer	Revised Project BETTER Flyer 7.18.22.docx	0.02	7/18/2022 5:41 PM	[name]	Recruitment/Advertising	Yes
View Consent form	Project BETTER Consent Form_revised 12.15.21.pdf	0.07	12/21/2021 10:35 AM	[name]	Consent/Assent/Information Sheet	Yes
View Informatics consult	BETTER_Informatics_Email.pdf	0.01	12/3/2021 9:57 AM	[name]	Other	Not Applicable
View PROC APPROVAL	BETTER_PROC_Approval.pdf	0.01	11/17/2021 1:27 PM	[name]	Ancillary Committee Approval	Not Applicable
View Study Notification Email Template	Project BETTER Study Notification Email Template.docx	0.01	11/17/2021 9:27 AM	[name]	Recruitment/Advertising	Yes
View Project Better Module Transcript	Project BETTER Peedy Transcript.docx	0.01	11/17/2021 9:24 AM	[name]	Research Measure	Yes
View Project BETTER Module Video Links	Project BETTER Video Links.docx	0.01	11/15/2021 12:02 PM	[name]	Other	Yes
View Project BETTER Brochure Webpage	Project BETTER Webpage.pdf	0.01	11/15/2021 12:01 PM	[name]	Other	Yes
View Project BETTER Overview	Project BETTER Technology-based Program Overview.pdf	0.01	11/15/2021 12:01 PM	[name]	Other	Yes
View Technology-based modules	Project BETTER Technology-based module links.docx	0.01	10/11/2021 7:42 PM	[name]	Other	Yes
View Brochure	Project BETTER Brochure.pdf	0.01	10/11/2021 7:41 PM	[name]	Research Measure	Yes
View Demographic questions	Project BETTER Demographic Questions .docx	0.01	10/11/2021 7:41 PM	[name]	Recruitment/Advertising	Yes
View RA forms 3	Project BETTER Study Visit 3 RA Form.docx	0.01	10/11/2021 7:40 PM	[name]	Research Measure	Yes
View RA forms 2	Project BETTER Study Visit 2 RA Form.docx	0.01	10/11/2021 7:39 PM	[name]	Research Measure	Yes
View RA forms 1	Project BETTER Study Visit 1 RA Form.docx	0.01	10/11/2021 7:39 PM	[name]	Research Measure	Yes
View Follow up survey 2	Project BETTER Follow-up Survey 2.docx	0.01	10/11/2021 7:39 PM	[name]	Research Measure	Yes
View Follow up survey 1	Project BETTER Follow-up Survey 1.docx	0.01	10/11/2021 7:39 PM	[name]	Research Measure	Yes
View Pre-survey	Project BETTER Pre-Survey.docx	0.01	10/11/2021 7:38 PM	[name]	Research Measure	Yes
View Chart abstraction form 3	Project BETTER Study Visit 3 Chart Abstraction Form.docx	0.01	10/11/2021 7:38 PM	[name]	Research Measure	Yes
View Chart abstraction form 2	Project BETTER Study Visit 2 Chart Abstraction Form.docx	0.01	10/11/2021 7:37 PM	[name]	Research Measure	Yes
View Chart abstraction	Project BETTER Study Visit 1 Chart Abstraction Form.docx	0.01	10/11/2021 7:37 PM	[name]	Research Measure	Yes

Document Name	Document	Version	Date Modified By	Uploaded Type	Approved
form 1					
View Scheduling and Reminder Scripts	Project BETTER Follow Up Scheduling 0.01 and Reminders Scripts.docx	0.01	10/11/2021 7:36 PM	[name] Study reminders/communications	Yes
View Follow up visit scripts	Project BETTER Follow-up Visits Script.docx	0.01	10/11/2021 7:36 PM	[name] Study reminders/communications	Yes
View [name] CV	CEM_CV_08.15.21_BT.pdf	0.01	10/10/2021 9:23 PM	[name] CV/Biosketch	Yes
View [name] CV	[name] CV .pdf	0.01	10/10/2021 5:44 PM	[name] CV/Biosketch	Not Applicable

Project Details

An intervention includes both physical procedures by which information or biospecimens are gathered (e.g., venipuncture) and manipulations of the subject or the subject's environment that are performed for research purposes.

An interaction includes communication or interpersonal contact between investigator and subject. It may include in-person, online, written, or verbal communications.

Secondary information/biospecimens are information or biospecimens that have been or will be collected for some other "primary" or "initial" activity and that will be used secondarily in the research study.

1. * Select all of the following types of interventions that apply to this study (selections will branch):

- Social/Behavioral interventions or experimentation / Tasks / Environmental manipulations
- Deception (misleading participants through false or incomplete information)
- Drug(s) / Biologics / Supplement(s) / Other Compounds (investigational products or products whose administration is dictated by the study protocol and not per the physician's clinical judgment)
- IV contrast administration for research-related imaging (will branch to the Drugs page)
- Placebos
- Safety and/or effectiveness evaluation of Bio-Medical Device(s), including in-vitro diagnostic devices/assays, mobile medical apps, software functions, and HUDs used in clinical investigations
- Washout Periods
- Expanded Access – Treatment Use of an Investigational Product
- Medical or Surgical Procedures (eg: physical exam, clinical procedures, scans, etc)
- Specimen/biological sample collection
- None of the Above

2. * Select all of the following types of interactions and methods of data collection that apply to this study (selections will branch):

- Surveys / Questionnaires / Written responses to questions (including data entry)
- Active Internet data collection (i.e. using the internet to collect data, including online surveys, data collection via Zoom, apps, etc.)
- Passive Internet data collection (i.e. passively observing online behavior, bots)
- Interviews / Focus Groups / Verbal responses to questions
- Audio / Video recording or photographing participants
- Observations
- Educational Settings/Assessments/Procedures
- None of the Above

3. * Select all types of secondary information and/or specimens that apply to this study (selections will branch):

See the help text for definitions.

- Individually Identifiable Health Information (PHI)
- Secondary data/specimens NOT from a research registry or repository
- Information/specimens from a research registry or repository (Usage Protocol)
- Information/specimens originally collected for a previous research study
- Publicly available information/specimens

- Government-generated or collected information that was or will be obtained for nonresearch activities [only applicable to research conducted by or on behalf of a Federal department or agency]
- No secondary data/specimens will be used

Behavioral Intervention/Task Details

This page asks for details about the social/behavioral intervention, task, or environmental manipulation in the research.

Interventions include both physical procedures by which information is gathered and manipulations of the subject or the subject's environment that are performed for research purposes. This might include activities such as playing computer games, performing a task, thought/cognition activities, environmental manipulations, and educational activities.

If the study only involves surveys, interviews, or secondary data collection, go back to the Project Details page and uncheck "Social/Behavioral interventions or experimentation / Tasks / Environmental manipulations" in Question 1.

1. * Describe the duration of the social/behavioral intervention, task, or environmental manipulation:

Module condition: Participants in the module condition will have access to the 3 modules in the technology-based intervention covering content on the pregnancy to postpartum transition, NOWS, and child welfare interactions (approximately 25-minutes each). Modules can be reviewed in the OB MOTIVATE clinic using research tablets or they can be reviewed remotely on a personal device in any order the participant chooses. Modules deliver information via the Computerized Intervention Authoring System, Version 3 (CIAS 3.0) using professionally produced videos and an interactive avatar using behavioral techniques, such as psychoeducation and aspects of motivational interviewing. Participants in the technology-based modules intervention condition will access the modules for 3 weeks through a link via email/text. Participants will enter their Study ID into the modules. No personal identifying information will be collected or housed in CIAS 3.0 modules. All participants in this condition will be oriented to the intervention with the RA via the program introduction (5 minutes).

Brochure condition: Provision of written materials to patients is often a component of standard care. Therefore, participants in the brochure condition will be provided a paper copy and/or provided an electronic pdf of the study brochure via email/text (in order to facilitate ease of participation for those who prefer remote study completion) covering content on the pregnancy to postpartum transition, NOWS, and child welfare interactions. There is a QR code within the brochure that leads to a website with additional information on the three educational topic areas. The participants will have 3 weeks to review the brochure content (including the additional educational content through the QR code). Review of all brochure information will take approximately 25-45 minutes.

2. * Describe any potential harms or discomforts that participants could experience during the intervention activity:

Few risks are expected by taking part in this study. There is the possibility that participants may experience some fatigue and/or discomfort when reviewing the content in the brochure or modules. The content in the brochure and modules is a review of information covered in standard medical treatment for this population. Participants will be informed of their right to refuse or stop study participation at any time, and their right to refuse to answer any questions that make them uncomfortable. The following message will also be provided in each of the modules and on the brochure, "If you have concerns or are experiencing a negative reaction to any of the content, please contact the research assistant at [contact]."

Participants may be disappointed if they are not assigned to their preferred group or are not able to access the technology-based modules throughout the study. Following the conclusion of the study, research team plans to make the technology-based modules accessible to clinicians and patients.

3. * Will the intervention activity be physically invasive or painful?

- Yes
- No

4. * Describe the impact the intervention activity will have on participants, including the nature and duration of any impact(s):

The brochure content will take approximately 25-45 minutes to review. The three modules each take approximately 25 minutes to review. Review of content based on study condition will take some sustained attention that will end after the content has been reviewed.

5. * In the investigator's opinion, is there any reason to think that the participants will find the intervention activity offensive or embarrassing? Explain why or why not.

No, the content in the brochure and modules is a review of information covered in standard medical treatment for this patient population. As part of standard prenatal care for people with opioid use disorder, medical providers review information about the pregnancy to postpartum transition, neonatal opioid withdrawal syndrome, and interactions with child welfare. The modules and brochure provide the same information using a different medium. Additionally, the brochure and modules were designed using a process of iterative modification grounded in formative data from both

patients and providers. Preliminary evaluation data indicate the modules and brochure are highly acceptable to patients and feasible to complete in a clinical setting and remotely. Based on our preliminary evaluation, no patients have found the modules or brochure to be offensive or embarrassing. In fact, some patients noted they are more comfortable receiving the information using the modules and brochure rather than being told directly from their medical provider.

Active Internet Data Collection

1. * Describe the platform/technology chosen for collecting the data and transmitting data securely over the internet. If proposing a non-VCU approved platform, give the rationale for selecting the technology instead of a VCU-approved platform.

RedCap, a VCU approved platform, will be used to store/collect all study visit data (surveys, RA questions, chart abstraction).

The Computerized Intervention Authoring System, Version 3 (CIAS 3.0) is an authoring tool that allows creation or editing of electronic screening and intervention packages without the need of a programmer. Interventions built using CIAS feature a synthetic text to speech engine that reads all questions and speaks aloud to the participant; synchronous interactivity, natural language reflections, branching logic, a clean user interface, and the ability to easily incorporate specific images, graphs, figures, text, or videos. CIAS applications are HIPAA compliant with encryption of all data in transit and at rest, and are hosted on a HIPAA-compliant cloud server. CIAS 3.0 is cross-platform compatible, meaning that it deploys readily on any device including those running the Android or Apple mobile operating systems. CIAS versions 1.0 and 2.0 have been used with thousands of participants, and consistently received extremely high satisfaction ratings (e.g., Naar-King et al., 2013; Ondersma et al., 2005, 2007, 2012), including with high risk and low SES samples.

For the current study, no identifiable data will be collected using the CIAS 3.0 software. Unique hyperlinks to the CIAS 3.0 modules, associated with participant study ID's, will be provided via email/text by the study RA.

2. * Describe how data will be linked or unlinked to identifiers including email addresses, names, and/or IP address.

A Study ID will be assigned to each participant upon study enrollment. All study visit data (survey, RA questions, chart abstraction) will be stored in RedCap and will only be labelled with participant's Study ID already associated with the study. The key linking the participant information and Study ID will be kept in a separate secure VCU RedCap database.

The participants will enter their Study ID into the CIAS platform when they complete the modules. Participants will not enter any identifying information into the modules.

A unique VCU email address used by the research team only will be used to send emails with the links for the RedCap surveys, modules, and the brochure.

3. * How will you protect your data collection from fraudulent responses:

Survey questionnaire links will not be publicly available. Each participant will be sent a RedCap link unique to their study ID to complete study questionnaires. Additionally, the RA will remind the participant that they can skip or not answer any questions that they would prefer not to answer and that they can end the survey at any time.

During brief RA-led questions, the RA will build rapport with participant to reduce stigma and encourage honest responses. Additionally, the RA will remind the participant that they can skip or not answer any questions that they would prefer not to answer and they can end the interview at any time.

Data checks for all data collection will be conducted regularly. Identified data irregularities will be discussed immediately with the PI and handled on a case by case basis.

In the CIAS intervention, attention check questions are included in each module.

4. * Is there an alternative method for completion of the data collection other than the internet?

Yes

No

5. * Describe how individuals will be able to skip or not answer particular questions. If any questions are mandatory, provide justification.

Participants will be able to skip or not answer particular questions if they choose by selecting "prefer not to answer."

6. If not including children, describe any procedures used to verify that research participants are adults.

All potential participants will be screened for eligibility (at least 18 years of age) by the research assistant (RA) using the OB MOTIVATE schedule and medical record. For potential participants that are not OB MOTIVATE patients, the RA will screen for eligibility when individuals are contacted. All eligibility criteria will be confirmed by the RA with the potential participant prior to study enrollment.

Secondary Data/Specimen Details

1. * Describe the source(s) and nature of the information/specimens being obtained. This response should:

- a. Identify where the data/specimens will come from (e.g., another researcher's registry, pathology lab, commercial source, medical records, etc.); and**
- b. List what types of specimens will be obtained (when applicable); and/or**
- c. List all data elements that will be obtained (when applicable). A data collection form or other documentation may be uploaded and referenced here.**

OB MOTIVATE patients:

- a. Data will be abstracted from the participants medical record for each study visit.
- b. No specimens will be obtained
